7.3.3. Serious Adverse Events

All SAEs, regardless of cause or relationship, that occur after the subject first consents to participate in the study (ie, signing the informed consent) and throughout the duration of the study, including the protocol-required post treatment follow-up period, must be reported in the eCRF database and Gilead Drug Safety and Public Health (DSPH) as instructed. This also includes any SAEs resulting from protocol-associated procedures performed after informed consent is signed.

Any SAEs and deaths that occur after the post treatment follow-up visit but within 30 days of the last dose of study drug, regardless of causality, should also be reported.

Investigators are not obligated to actively seek SAEs after the 30-day period. However, if the investigator learns of any SAEs that occur after study participation has concluded and the event is deemed relevant to the use of study drug, he/she should promptly document and report the event to Gilead DSPH.

All AEs and SAEs will be recorded in the eCRF database within the timelines outlined in the eCRF completion guideline.

7.3.4. Electronic Serious Adverse Event (eSAE) Reporting Process

- Site personnel record all SAE data in the eCRF database and from there transmit the SAE information to Gilead DSPH within 24 hours of the investigator's knowledge of the event. Detailed instructions can be found in the eCRF completion guidelines.
- If for any reason it is not possible to record the SAE information electronically, ie, the eCRF database is not functioning, record the SAE on the paper SAE reporting form and submit within 24 hours of the investigator's knowledge of the event to:

Gilead DSPH: Fax: PPD
 Email: PPD

- As soon as it is possible to do so, any SAE reported via paper must be transcribed into the eCRF Database according to instructions in the eCRF completion guidelines.
- If an SAE has been reported via a paper form because the eCRF database has been locked, no further action is necessary.
- All AEs and SAEs will be recorded in the eCRF database within the timelines outlined in the eCRF completion guideline.
- For fatal or life-threatening events, copies of hospital case reports, autopsy reports, and other documents are also to be submitted by e-mail or fax when requested and applicable. Transmission of such documents should occur without personal subject identification, maintaining the traceability of a document to the subject identifiers.
- Additional information may be requested to ensure the timely completion of accurate safety reports.
- Any medications necessary for treatment of the SAE must be recorded onto the concomitant medication section of the subject's eCRF and the event description section of the SAE form

7.4. Gilead Reporting Requirements

Depending on relevant local legislation or regulations, including the applicable US FDA Code of Federal Regulations, the EU Clinical Trials Directive (2001/20/EC) and relevant updates, and other country-specific legislation or regulations, Gilead may be required to expedite to worldwide regulatory agencies reports of SAEs, SADR, or suspected unexpected serious adverse reactions (SUSARs). In accordance with the EU Clinical Trials Directive (2001/20/EC), Gilead or a specified designee will notify worldwide regulatory agencies and the relevant IEC in concerned Member States of applicable SUSARs as outlined in current regulations.

Assessment of expectedness for SAEs will be determined by Gilead using reference safety information specified in the investigator's brochure or relevant local label as applicable.

All investigators will receive a safety letter notifying them of relevant SUSAR reports associated with any study drug. The investigator should notify the IRB or IEC of SUSAR reports as soon as is practical, where this is required by local regulatory agencies, and in accordance with the local institutional policy.

7.4.1. Reporting of Adverse Events Relating to the Primary Endpoint and Other Anticipated Medical Events in the Study Population

Given the endpoints of the study, in order to maintain the integrity of the study, the following events that are assessed as unrelated to study drug will not be considered SAEs:

- Progression of disease
- Death related to progression of disease

Disease progression and death from disease progression should be reported as SAEs by the investigator only if it is assessed that the study drug caused or contributed to the disease progression (ie, by a means other than lack of effect). Unrelated disease progression should be captured on the eCRF.

7.5. Toxicity Management

Treatment-emergent toxicities will be noted by the Investigator and brought to the attention of the Gilead Sciences Medical Monitor or designee. Whether or not considered treatment-related, all subjects experiencing AEs must be monitored periodically until symptoms subside, any abnormal laboratory values have resolved or returned to baseline levels or they are considered irreversible, or until there is a satisfactory explanation for the changes observed.

Grade 3 or 4 clinically significant laboratory abnormalities should be confirmed by repeat testing as soon as practical to do so, and preferably within 3 calendar days after receipt of the original test results. Any questions regarding toxicity management should be directed to the Gilead Sciences Medical Monitor or designee.

7.6. Special Situations Reports

7.6.1. Definitions of Special Situations

Special situation reports include all reports of medication error, abuse, misuse, overdose, reports of AEs associated with product complaints, and pregnancy reports regardless of an associated AE. Reports of adverse reactions in infants following exposure from breastfeeding, and reports of adverse reactions associated with product complaints and reports arising from occupational exposure are also considered special situation reports.

- A pregnancy report is used to report any pregnancy in female subjects only, or female partners of male subjects on study
- Medication error is any unintentional error in the prescribing, dispensing, or administration of a medicinal product while in the control of the health care provider, subject, or consumer
- Abuse is defined as persistent or sporadic intentional excessive use of a medicinal product by a subject
- Misuse is defined as any intentional or inappropriate use of a medicinal product that is not in accordance with the protocol instructions or the local prescribing information
- An overdose is defined as an accidental or intentional administration of a quantity of a medicinal product given per administration or cumulatively which is above the maximum recommended dose as per protocol or in the product labelling (as it applies to the daily dose of the subject in question). In cases of a discrepancy in drug accountability, overdose will be established only when it is clear that the subject has taken the excess dose(s). Overdose cannot be established when the subject cannot account for the discrepancy except in cases in which the investigator has reason to suspect that the subject has taken the additional dose(s)
- Product complaint is defined as complaints arising from potential deviations in the manufacture, packaging, or distribution of the medicinal product

7.6.2. Instructions for Reporting Special Situations

7.6.2.1. Instructions for Reporting Pregnancies

The investigator should report pregnancies in female study subjects that are identified after initiation of study medication and throughout the study, including the post study drug follow-up period, to Gilead DSPH using the pregnancy report form within 24 hours of becoming aware of the pregnancy. Refer to the eCRF completion guidelines for full instructions on the mechanism of pregnancy reporting.

The pregnancy itself is not considered an AE nor is an induced elective abortion to terminate a pregnancy without medical reasons.

Any premature termination of pregnancy (eg, a spontaneous abortion, an induced therapeutic abortion due to complications or other medical reasons) must be reported within 24 hours as an SAE. The underlying medical reason for this procedure should be recorded as the AE term.

A spontaneous abortion is always considered to be an SAE and will be reported as such. Furthermore, any SAE occurring as an adverse pregnancy outcome post study must be reported to Gilead DSPH.

The subject should receive appropriate monitoring and care until the conclusion of the pregnancy. The outcome should be reported to Gilead DSPH using the pregnancy outcome report form. If the end of the pregnancy occurs after the study has been completed, the outcome should be reported directly to Gilead DSPH.

Pregnancies of female partners of male study subjects exposed to Gilead or other study drugs must also be reported and relevant information should be submitted to or Gilead DSPH using the pregnancy and pregnancy outcome forms within 24 hours. Monitoring of the subject should continue until the conclusion of the pregnancy. If the end of the pregnancy occurs after the study has been completed, the outcome should be reported directly to Gilead DSPH.

Gilead DSPH: Fax: PPD
Email: PPD

Refer to [Appendix 7](#) for Pregnancy Precautions, Definition for Female of Childbearing Potential, and Contraceptive Requirements.

7.6.2.2. Reporting Other Special Situations

All other special situation reports must be reported on the special situations report form and forwarded to Gilead DSPH within 24 hours of the investigator becoming aware of the situation. These reports must consist of situations that involve study drug and/or Gilead concomitant medications, but do not apply to non-Gilead concomitant medications.

Special situations involving non-Gilead concomitant medications does not need to be reported on the special situations report form; however, for special situations that result in AEs due to a non-Gilead concomitant medication, the AE should be reported on the AE form.

Any inappropriate use of concomitant medications prohibited by this protocol should not be reported as “misuse,” but may be more appropriately documented as a protocol deviation.

Refer to the eCRF completion guidelines for full instructions on the mechanism of special situations reporting.

All clinical sequelae in relation to these special situation reports will be reported as AEs or SAEs at the same time using the AE eCRF and/or the SAE report form. Details of the symptoms and signs, clinical management, and outcome will be reported, when available.

8. STATISTICAL CONSIDERATIONS

8.1. Analysis Objectives and Endpoints

8.1.1. Analysis Objectives

The primary objectives of this study are:

- Characterize the safety and tolerability of GS-5829 as a monotherapy in subjects with advanced solid tumors and lymphomas
- Determine the MTD or RDP2 of GS-5829 as a monotherapy in subjects with advanced stage solid tumors and lymphomas
- Characterize the safety and tolerability of GS-5829 in combination with exemestane or fulvestrant in subjects with advanced estrogen receptor positive breast cancer
- Determine MTD or RDP2 of GS-5829 in combination with exemestane or fulvestrant in subjects with advanced estrogen receptor positive breast cancer

8.1.2. Primary Endpoint

The primary endpoint of this study is incidence of DLT as defined in Section 3.2.

8.1.3. Secondary Endpoint

Secondary endpoints of this study are:

- PK parameters (C_{max} , C_{tau} , AUC_{last} , AUC_{tau} , T_{max} , and $t_{1/2}$) for GS-5829.

CCI

[REDACTED]

[REDACTED]

[REDACTED]

[REDACTED]

8.2. Analysis Conventions

8.2.1. Analysis Sets

8.2.1.1. Full Analysis Set (FAS)

The FAS includes all subjects who receive ≥ 1 dose of study drug (GS-5829, exemestane or fulvestrant). This analysis set will be used for subject characteristics and efficacy endpoints.

8.2.1.2. Safety Analysis Set

The Safety Analysis Set for this study will be the same as FAS since this study is a non-randomized study. This analysis set will be used for safety endpoints, study treatment administration and post-study therapy.

8.2.1.3. DLT-Evaluable Analysis Set

The DLT-Evaluable Analysis Set includes all subjects in the Safety Analysis Set who complete all treatment and safety procedures through Day 29, or experienced a DLT prior to Day 29. Determination of the MTD will be in DLT-Evaluable Analysis Set.

8.2.1.4. Pharmacodynamic and Pharmacokinetic Analysis Sets

The **CCI** PK Analysis Sets consist of all subjects in the FAS who have the necessary baseline and on-study measurements to provide interpretable results for the specific parameters of interest.

CCI

8.3. Data Handling Conventions

By-subject listings will be created for important variables from each eCRF module. Summary tables for continuous variables will contain the following statistics: N (number in population), n (number with data), mean, standard deviation (StD), 90% confidence intervals (CIs) on the mean, median, minimum, and maximum. Summary tables for categorical variables will include: N, n, percentage, and 90% CIs on the percentage. Unless otherwise indicated, 90% CIs for binary variables will be calculated using the binomial distribution (exact method) and will be 2-sided. Data will be described and summarized by relevant study group, dose level, analysis set, and time point. As appropriate, changes from baseline to each subsequent time point will be described and summarized by study group and dose level. Similarly, as appropriate, the best change from baseline during the study will also be described and summarized by study group and dose level. Graphical techniques (eg, waterfall plots, Kaplan-Meier curves, line plots) may be used when such methods are appropriate and informative.

The baseline value will be the last (most recent) pre-treatment value. Data from all sites will be pooled for all analyses. Analyses will be based upon the observed data unless methods for handling missing data are specified. If there is a significant degree of non-normality, analyses may be performed on log-transformed data or nonparametric tests may be applied, as appropriate.

8.4. Demographic Data and Baseline Characteristics

Subject demographic and baseline characteristics will be listed and summarized by study group and dose level for the Safety Analysis Set.

8.5. Efficacy Analysis

ORR and PFS will be listed only.

8.6. Safety Analysis

All safety data collected on or after the date that study drug (GS-5829, exemestane or fulvestrant) was first dispensed up to the date of last dose of study drug plus 30 days will be summarized by study group and dose level. Data for the pretreatment will be included in data listings.

8.6.1. Extent of Exposure

Descriptive information will be provided by study group and dose level regarding the number of doses of study drug prescribed (GS-5829, exemestane or fulvestrant), the total number of doses taken, the percent of expected doses taken, the number of days of study drug, and the number and timing of prescribed dose modification and interruptions.

GS-5829 compliance will be described by study group and dose level in terms of the proportion of study drug actually taken based on returned pill count relative to the amount that was dispensed (taking into account physician-prescribed modification and interruptions).

8.6.2. Adverse Events

All AEs will be listed. The focus of AE summarization will be on treatment-emergent AEs. A treatment-emergent AE is defined as an AE that occurs or worsens in the period from the first dose of study drug (GS-5829, exemestane or fulvestrant) to 30 days after the last dose of study drug.

AEs will be coded using the Medical Dictionary for Regulatory Activities (MedDRA <http://www.meddrasso.com>) with descriptions by System Organ Class (SOC), High-Level Group Term, High-Level Term, Preferred Term, and Lower-Level Term. The severity of AEs will be graded by the investigator according to the CTCAE, Version 4.03, whenever possible. If a CTCAE criterion does not exist for a specific type of AE, the grade corresponding to the appropriate adjective will be used by the investigator to describe the maximum intensity of the AE: Grade 1 (mild), Grade 2 (moderate), Grade 3 (severe), Grade 4 (life threatening), or Grade 5 (fatal). The relationship of the AE to the IP will be categorized as related or unrelated.

TEAEs will be summarized by dose level. Summary tables will be presented to show the number of subjects reporting treatment-emergent AEs by severity grade and corresponding percentages. A subject who reports multiple treatment-emergent AEs within the same Preferred Term (or SOC) is counted only once for that Preferred Term (or SOC) using the worst severity grade. AE descriptions will be presented by decreasing frequency for a given SOC and Preferred Term. Separate listings and summaries will be prepared for the following types of treatment emergent AEs:

- Study-drug-related (GS-5829, exemestane or fulvestrant) AEs
- AEs that are Grade ≥ 3 in severity
- AEs leading to study drug (GS-5829, exemestane or fulvestrant) interruption and/or dose modification
- AEs leading to study drug (GS-5829, exemestane or fulvestrant) discontinuation
- SAEs

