The SRT will consist of at least one investigator and the following:
Gilead Sciences, Inc. (Gilead) study team members: the medical monitor, representatives from Drug Safety and Public Health (DSPH), Clinical Operations, and Biostatistics. Others may be invited to participate as members of the SRT if additional expertise is desired. The medical monitor serves as the chair of the SRT.

Prior to initiating enrollment for Dose Level 4 in Group 1, an analysis of all available safety, PK, and PD data from previous cohorts will be reviewed.

If a subject is enrolled in a dose level but does not complete the PK or PD analysis, they may continue on study but an additional subject may be enrolled at that dose level.

The MTD is the highest dose level with a subject incidence of ≤ 1 DLT during the first 28 days of study drug dosing of 6 subjects. A minimum of 6 subjects need to be treated at a dose level before this dose level can be deemed as the MTD.

Group 2: Combination therapy of GS-5829 with exemestane or fulvestrant in patients with advanced stage estrogen receptor positive breast cancer

Cohorts of subjects with advanced estrogen receptor positive breast cancer for whom no standard curative therapy exists and who are candidates for exemestane or fulvestrant will be sequentially enrolled at progressively higher dose levels of oral GS-5829 in combination with full standard doses of exemestane or fulvestrant. The starting dose of GS-5829 will be 2.0 mg QD, which is a dose level that has been demonstrated to be safe and tolerable (no Grade 2 or higher drug related toxicity) in patients with solid tumors and prostate cancer. Dose escalation will continue with cohort sizes of 3-6 subjects in parallel arms: Group 2A will initiate with 2.0 mg of GS-5829 orally once daily on Cycle 1 Day 1 combined with 25 mg of exemestane once daily beginning on Cycle 1 Day 1. The subject may initiate exemestane anytime prior to, or on, Cycle 1 Day 1. Group 2B will initiate with 2.0 mg of GS-5829 orally once daily on Cycle 1 Day 1 with 500 mg fulvestrant administered intramuscularly (Cycle 1 Day 1 and then every 28 days (+/- 3 days)). If Cycle 1 Day 1 is the subject's first dose of fulvestrant, a one-time additional dose of fulvestrant should be administered on Cycle 1 Day 15).

The doses for each candidate dose level in group 2 are shown in [Table 3-2](#).

Table 3-2. Group 2: Combination of GS-5829 in Breast Cancer

Dose Level	GS-5829*	Group 2A Exemestane	Group 2B Fulvestrant

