4.3. Exclusion Criteria

Subjects who meet *any* of the following exclusion criteria are not to be enrolled in this study.

- 1) History or evidence of clinically significant disorder, condition, or disease that, in the opinion of the Investigator or Medical Monitor would pose a risk to subject safety or interfere with the study evaluations, procedures, or completion
- 2) Pregnant
- 3) Known brain metastasis or leptomeningeal disease

- 4) Uncontrolled intercurrent illness including, but not limited to, active uncontrolled infection, active or chronic bleeding event within 28 days prior to first dose of study drug, uncontrolled cardiac arrhythmia, or psychiatric illness/social situation that would limit compliance with study requirements as judged by treating physician
- 5) Myocardial infarction, symptomatic congestive heart failure (New York Heart Association Classification > Class II), unstable angina, or serious uncontrolled cardiac arrhythmia within the last 6 months of study Day 1
- 6) Major surgery, defined as any surgical procedure that involves general anesthesia and a significant incision (ie, larger than what is required for placement of central venous access, percutaneous feeding tube, or biopsy) within 28 days of first dose of study drug
- 7) Impairment of gastrointestinal (GI) function or GI disease that may significantly alter the absorption of GS-5829, including any unresolved nausea, vomiting, or diarrhea that is Common Terminology Criteria for Adverse Events (CTCAE) Grade >1
- 8) Minor surgical procedure(s) within 7 days of enrollment or randomization, or not yet recovered from prior minor surgery (placement of central venous access device, fine needle aspiration, or endoscopic biliary stent \geq 1 day before enrollment or randomization is acceptable)
- 9) Anti-tumor therapy (chemotherapy, antibody therapy, molecular targeted therapy) within 21 days or 5 half-lives, whichever is longer, of study drug dosing (6 weeks for nitrosoureas, mitomycin C, or molecular agents with $t_{1/2} > 10$ days); concurrent use of hormone therapy for prostate cancer is permitted, and concurrent use of exemestane or fulvestrant (and goserelin for pre/perimenopausal breast cancer as per inclusion criteria 2.c.iv) for subjects enrolled in Group 2 (advanced breast cancer) is permitted

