Faslodex[®] (fulvestrant) is supplied as 50 mg/mL for intramuscular administration. Subjects assigned to receive fulvestrant in combination with GS-5829 in this study will receive fulvestrant on Cycle 1 Day 1 and every 28 days (+/- 3 days) until the end of treatment. For subjects initiating fulvestrant on this study, a single additional dose of fulvestrant 500 mg should be administered on Cycle 1 Day 15 (+/- 3 days). Fulvestrant should be administered intramuscularly into the buttocks slowly (1 – 2 minutes per injection) as two 5mL injections, one in each buttock. Refer to [Appendix 10](#) for further details.

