6. STUDY PROCEDURES

The study procedures to be conducted for each subject enrolled in the study are presented in tabular form in [Appendix 2](#) and described in the text below.

The investigator must document any deviation from protocol procedures and notify the sponsor or contract research organization (CRO).

Safety and tolerability assessments will include regular monitoring of AEs, changes from baseline in laboratory variables, physical examinations, vital signs, and special safety assessment like ECGs.

From the time of obtaining informed consent through the first administration of investigational medicinal product, record all serious adverse events (SAEs), as well as any non-serious AEs related to protocol-mandated procedures on the AEs electronic case report form (eCRF). All other untoward medical occurrences observed during the Screening period, including exacerbation or changes in medical history are to be captured on the medical history eCRF. See Section 7 for additional details.

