8.6.3. Laboratory Evaluations

All laboratory data will be listed. Summaries of laboratory data will be based on observed data. The focus of laboratory data summarization will be on treatment-emergent laboratory abnormalities. A treatment-emergent laboratory abnormality is defined as an abnormality that, compared to baseline, worsens by ≥ 1 grade in the period from the first dose of study drug (GS-5829, exemestane or fulvestrant) to 30 days after the last dose of study drug. If baseline data are missing, then any graded abnormality (ie, an abnormality that is Grade ≥ 1 in severity) will be considered treatment emergent.

Hematological, serum biochemistry, and urine data will be programmatically graded according to CTCAE severity grade, when applicable. For parameters for which a CTCAE scale does not exist, reference ranges from the central laboratory will be used to determine programmatically if a laboratory parameter is below, within, or above the normal range for the subject's age, sex, etc. Hematological and serum biochemistry and their changes from baseline will be summarized by study group, dose level, and visit. Summary tables will be presented for each relevant assay to show the number of subjects by CTCAE severity grade with corresponding percentages. For parameters for which a CTCAE scale does not exist, the frequency of subjects with values below, within, and above the normal ranges will be summarized. Subjects will be characterized only once for a given assay, based on their worst severity grade observed during a period of interest (eg, during the study or from baseline to a particular visit).

Shift tables for hematology and serum biochemistry will also be presented by showing change in CTCAE severity grade from baseline to the worst grade post-baseline. For parameters for which a CTCAE scale does not exist, shift tables will be presented showing change in results from baseline to the worst grade post baseline. Separate listings and summaries will be prepared for laboratory abnormalities that are Grade ≥ 3 in severity.

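### Does the protocol's three-drug meaning of study drug move the Group 2 safety windows ahead of GS-5829?

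*Protocol*

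**What the plan says.** The protocol's statistical section spells out three drugs in four places.

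- Section 8.2.1.1 admits to the Full Analysis Set anyone with at least one "dose of study drug (GS-5829, exemestane or fulvestrant"). Section 8.2.1.2 makes the Safety Analysis Set the same.
- Section 8.6 summarises "All safety data collected on or after the date that study drug (GS-5829, exemestane or fulvestrant) was first dispensed", up to 30 days after the last dose.
- Section 8.6.2 sets the adverse-event window as "in the period from the first dose of study drug (GS-5829, exemestane or fulvestrant) to 30 days after the last dose of study drug".
- Section 8.6.3 uses the same window for laboratory abnormalities and adds: "If baseline data are missing, then any graded abnormality" counts as treatment-emergent.

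On Group 2 dosing, section 3.2 says: "The subject may initiate exemestane anytime prior to, or on, Cycle 1 Day 1". Section 4.3 permits "concurrent use of exemestane or fulvestrant". Section 5.3 has a rule "For subjects initiating fulvestrant on this study", which implies that others arrive already treated. The Test Product entry of the synopsis instead starts exemestane on C1D1. The sponsor must reconcile these passages; the check below allows for either.

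The SAP writes study drug without listing drugs: section 3.1.2 (Full Analysis Set), 3.8.1 (study day), 6.1.1.1 (PFS origin), 7.1.5.1 (treatment-emergent events), 7.2.1 (laboratory baseline) and 7.2.2.1 (laboratory window). SAP section 7.7 reports no departure from the protocol's safety analyses.

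**The concern.** Safety of the combination is a primary objective, and it will be read from Group 2 tables by dose level in cohorts of 3 to 6. If the clock starts with endocrine therapy, events and laboratory abnormalities from before the first GS-5829 dose could be tabulated against a GS-5829 dose level.

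The laboratory case looks sharpest. Screening chemistry and hematology are drawn within 7 days of C1D1 (Appendix 2, note s). A subject on exemestane for longer than that would have no scheduled value before the first dose of any of the three drugs. The missing-baseline rule would then turn a stable entry abnormality into a treatment-emergent one. Such entry values are allowed: section 4.2 accepts ALT/AST up to 5 x ULN with liver metastases, which lies in the Grade 2 band of Table 6-2. With no definition in the SAP, two programmers could apparently derive different tables.

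**Working it through.** **1. What the three-drug reading would do.** Let L be the number of days by which endocrine therapy precedes C1D1. The documents give no value for L, so it is assumed here over a range. By SAP section 3.8.1, C1D1 becomes study day L + 1. A scheduled laboratory value exists on or before the first dose only if L ≤ 7. For a subject who takes GS-5829 for 28 days and stops all drugs together, the window lasts 28 + 30 + L days.

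| L (assumed) | Study day of C1D1 | Scheduled lab baseline? | Window, days |
|---|---|---|---|
| 0 | 1 | yes | 58 |
| 7 | 8 | yes | 65 |
| 8 | 9 | no | 66 |
| 14 | 15 | no | 72 |
| 28 | 29 | no | 86 |

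With GS-5829 as the anchor, every row reads 1, yes, 58. The PFS origin would move in the same way, by L/7 weeks (28/7 = 4.0 weeks at L = 28).

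**2. Size per affected subject.** 1/3 = 33.3 points in a cohort of 3 and 1/6 = 16.7 points in a cohort of 6. That is what any one subject contributes to a cohort of that size; it is not an estimate of bias. SAP section 1.3 reports 33 enrolled. Protocol section 1.3.3 places at least 4 in Group 1, so Group 2 had at most 33 − 4 = 29. SAP section 8.1 lists Group 1 cohorts up to 6. If cohorts 5 and 6 ran with at least 3 subjects each, Group 1 had at least 4 + 3 + 3 = 10, and Group 2 at most 33 − 10 = 23. How many of these had any lead-in is not stated and may be none.

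**3. Which reading the SAP follows.**

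- Section 3.6.1 sends a missing last study-drug date to section 4.2.1, which derives first and last dosing dates for exposure to GS-5829.
- Sections 4.2 and 4.2.2.1 use GS-5829 and study drug interchangeably.
- Section 7.1.6.1 ties relatedness, discontinuation, interruption and dose-reduction tables to GS-5829 alone.

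**4. Which reading the schedule follows.**

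- The synopsis (Screening) and protocol section 5.1 place the first study-drug dose on Study Day 1/C1D1 or Day 1.
- Appendix 2, note b, makes C1D1 the first day of study for every Group 2 cohort. The endocrine-therapy row of that table has its first mark at C1D1.
- Section 5.1 requires baseline tests to be finished before the first study-drug dose. With laboratory draws tied to the 7 days before C1D1, a subject with a longer lead-in could not comply if exemestane counted.
- The safety call in section 6.4.1 is timed from the last GS-5829 dose, which also suggests which drug closes the window.

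**5. Adverse events.** Section 6 restricts recording to serious and procedure-related events "From the time of obtaining informed consent through the first administration of investigational medicinal product". If that product means GS-5829, the window opens at C1D1 and the shift is 0. If it means any of the three drugs, section 7.3.2 starts full collection with the endocrine drug once consent is given, and the restriction no longer limits anything. Opening the window with one meaning and limiting collection with the other produces a rule that no passage states.

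**6. Laboratory values.** A false treatment-emergent grade needs all four of these: the three-drug meaning applied to baseline; L above 7; no usable unscheduled pre-dose value, which SAP section 3.8.2 would accept; and a Grade 1 or higher value at entry. Protocol section 8.3 defines baseline as the latest pre-treatment value and does not name the three drugs.

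**The case for a change.** The best case for a change is that the protocol's parenthesis is explicit and repeated, whereas the C1D1 passages concern visit timing. Exemestane and fulvestrant are described under the investigational products heading of protocol section 5. SAP section 7.4.2 refers to study drugs in the plural. SAP section 7.7 claims no departures even though section 7.1.6.1 already narrows the protocol's related-event and discontinuation tables from three drugs to GS-5829, so 7.7 cannot settle the meaning. One sentence would remove the doubt at almost no cost.

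Some of this stands. There is no formal definition, the statement in 7.7 is loose, and exemestane before C1D1 is plainly allowed in sections 3.2 and 5.3. The point is weaker for fulvestrant, because its study schedule starts on C1D1 and earlier doses count only if pre-study treatment is treated as study drug.

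What does not stand is that the two derivations are equally open. The narrowing in section 7.1.6.1 is itself evidence that the SAP works with GS-5829, and section 3.6.1 identifies the dosing dates by cross-reference. The plural in 7.4.2 only keeps protocol drugs out of a concomitant-medication listing.

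**Conclusion.** This is a missing definition that analysts fill sensibly. With first and last study-drug dose taken as GS-5829, which SAP usage and the schedule both support, baseline, study day and the treatment-emergent windows are the same for any endocrine lead-in, and the shift is 0. The 33- and 17-point figures apply only to a subject who meets every condition of the other reading, and nothing in the documents shows that such a subject exists.

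The reach is limited to descriptive Group 2 summaries with no formal testing. Nothing follows for Full Analysis Set denominators, since SAP section 3.2 groups subjects by treatment actually received, nor for dose-limiting toxicity, the MTD, or Groups 1 and 3. All adverse events are listed with a treatment-emergent flag (SAP section 7.1.6.1), so a reader could see any early event. A clarifying sentence in the SAP or study report would do no harm, but no result depends on it. The conclusion assumes that the programmers follow the SAP's own usage.
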